## 5.10 Study Duration

The subject will participate for 6 months from the initial consent.

We expect that enrollment to the study will be for a period of 1 months.

## 5.11 Data to Capture

### 5.11.1 Required Data

All required data for this study will be collected via paper and or electronic case report forms (eCRF).

### 5.11.2 Data Collection

The final set of CRFs is designed to accommodate the specific features of the trial design. Modification of CRFs will only be made if deemed necessary by Soroka CRC. The CRFs will be filled out manually by the study personal and or will be collected through the computer services database.

The following data will be collected:

- Demographic data: age, sex, country of birth, healthcare profession, direct contact with covid subjects in working capacity.
- Detailed medical history, including but not limited to past illness with COVID, malignancy, diabetes, renal failure, heart disease, hypertension, history of stroke, rheumatological illness.
- Current medications used and medications used for more than one week in the past three months.
- Any adverse event during the study as a result of vaccination.

## 6 Statistical Considerations and Analysis Plan

In this prospective observational registry we aim to assess the rates of the COVID-19 infection as confirmed by PCR testing or positive serology for N antigen during the follow up period. We hypothesize that booster of BNT162b2 vaccine in healthcare workers (HCW) will lower the rates of the COVID-19 infection as compared to HCW choosing not to receive the second booster.

We aim to enroll up to 1000 subjects. The following assumptions were used to estimate the power of the analysis.

- The proportion of the HCW choosing to receive the second booster is 60%
- The expected monthly infection rate of 2.5% in the non-vaccinated group
- Expected monthly infection rate of 1.0% in the treatment group
- Median follow-up until switching to the booster administration in the non-vaccinated group (15%) of 4 months
- Type I error ( $\alpha$ ) = 0.025 (one-sided)
- Log-rank test
- Enrollment period of 1 month
- Lost to follow-up of 10%

An evaluable sample size of 1000 subjects provides 80.0% power to reject the null hypothesis, signifying the booster strategy is superior to the comparison group at 6 months post-vaccination.

All statistical analyses will be performed using Statistical Analysis System (SAS) for Windows (version 9.4 or higher, SAS Institute Inc. Cary, NC) or other widely accepted statistical or graphical software. In general, data for all study patients will be combined and presented. Individual data will be presented in patient listings.

Descriptive statistics will be used to present the data and to summarize the results. Categorical variables will be presented using frequency distributions and cross tabulations with numbers and percent per group. Continuous variables will be summarized by presenting the number of observations (N), mean, 95% confidence interval of the mean, standard deviation, median, minimum, and maximum values.

The primary outcome will be analyzed within the paradigm of the survival analysis, i.e. log-rank test for the univariate analysis. Since it is possible that those who chose not to be vaccinated will differ in a number of characteristics, we will utilize Cox regression models with time dependent variable (timing of the booster) with the adjustment for the potential confounders. The confounders will be identified by the DAG approach. In addition different approaches to approximate the counterfactual world assumption such as propensity score adjustment will be considered.

The following subgroup analysis will be performed: stratified by age, gender, immune status, medical center, timing of the booster (before and after the current wave peak).

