## 5.4 Flow chart

Subjects in the control group who are vaccinated after inclusion in the study with a fourth dose will be switched to the vaccinated arm and followed from that point as boosted.

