#### **5.5.3 Withdrawal/Discontinuation Criteria**

All subjects should be encouraged to remain in the study through the entire follow up. However, if a subject decides to discontinue study participation, the reason for discontinuation must be recorded in the medical record and the Case Report Form (CRF). Subjects who discontinue participation prematurely will be included in the analysis of results (as appropriate) but they will not be replaced in the enrollment of total study subjects.

Every attempt must be made to have all subjects complete the follow up visit schedule. A subject will not be considered lost-to-follow up unless all efforts to obtain compliance are unsuccessful.

Discontinuation in the study will be if the antibody result at enrollment visit shows the participant already had the disease.

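### The stated 80.0% power does not follow from the listed inputs under the protocol's own rule for switchers, which gives about 95–99%; the switching input and the 'evaluable' 1000 are also unclear

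*Protocol*

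**What the plan says.** Section 6, repeated in the sample size row of section 2, lists the power inputs: 60% choose the booster; infection is 2.5% per month without it and 1.0% with it; one-sided type I error 0.025; log-rank test; 1 month of enrolment; 10% lost. Switching enters as "Median follow-up until switching to the booster administration in the non-vaccinated group (15%) of 4 months". The conclusion is "An evaluable sample size of 1000 subjects provides 80.0% power to reject the null hypothesis", at 6 months.

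Section 5.4 says controls who take the fourth dose after inclusion "will be switched to the vaccinated arm and followed from that point as boosted". For the adjusted analysis, section 6 says "we will utilize Cox regression models with time dependent variable (timing of the booster" as the time-dependent term.

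On numbers, section 6 says "We aim to enroll up to 1000 subjects". Section 5.5.3 says early leavers "will be included in the analysis of results (as appropriate) but they will not be replaced in the enrollment of total study subjects", and adds: "Discontinuation in the study will be if the antibody result at enrollment visit shows the participant already had the disease".

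**The concern.** A fall from 2.5% to 1.0% per month is a hazard ratio of about 0.40. With 1000 people followed for 6 months, that effect should be detected with far more than 80% power unless something dilutes it strongly. The only listed input that could do so is switching, and switching dilutes strongly only if switchers go on being counted as unboosted. Section 5.4 says the opposite.

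Two things are at stake. First, this paragraph is the only justification of the study's size, and a reader will take 2.5% against 1.0% as the effect detectable with 80% power. Second, if 80.0% came from an analysis by initial choice, the study was sized for a different comparison (initial choice) from the one it plans (boosted against unboosted time).

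The switching line and the word 'evaluable' add to the difficulty, because neither can be read in only one way.

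**Working it through.** **Inputs (section 6; follow-up from section 5.10).** Constant hazards are assumed.
- Unboosted: h0 = −ln(0.975) = 0.02532 per month. Boosted: h1 = −ln(0.99) = 0.01005. HR = 0.397.
- Allocation 60:40; follow-up 6 months each; one-sided 0.025, so z = 1.96.
- Loss: 10% over 6 months, hazard −ln(0.9)/6. The period is not stated, so this is an assumption.
- Switching hazard s in controls, three readings: 15% in total, −ln(0.85)/6; median 4 months, ln2/4; 15% per month, −ln(0.85) = 0.1625, whose median is ln2/0.1625 = 4.27 months. Because 4.27 is close to 4, both a total and a monthly share are plausible.

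**Step 1: no switching, no loss.** Events = 600 × (1 − 0.99^6) + 400 × (1 − 0.975^6) = 35.1 + 56.4 = 91.5. Schoenfeld power = Φ(√(91.5 × 0.6 × 0.4) × |ln 0.397| − 1.96) = Φ(4.33 − 1.96) = 99.1%. About 39 events suffice for 80%.

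**Step 2: with switching and loss.** Numbers at risk, each multiplied by the retention factor exp(−loss hazard × t):
- initially boosted: B = 0.6N·exp(−h1·t)
- controls not yet switched: C = 0.4N·exp(−(h0+s)t)
- switched controls, at hazard h1: S = 0.4N·s·exp(−h1·t)(1 − exp(−kt))/k, with k = h0 + s − h1

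Under section 5.4 the groups are B+S and C. By initial choice they are B and C+S. With q the boosted share at risk, e1 the boosted event rate and e the total event rate, U = ∫(e1 − q·e)dt, V = ∫q(1−q)e dt, and power = Φ(|U|/√V − 1.96).

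Examples, N = 1000:
- Section 5.4, 15% in total: 19.10/√19.46 = 4.33; power 99.1%, 84.6 events.
- Section 5.4, median 4 months: 14.98/√13.79 = 4.03; power 98.1%, 75.4 events.
- Initial group, median 4 months: 12.45/√17.98 = 2.94; power 83.6%, 75.4 events.

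All cells, integration / simulation of 4000 trials. The N = 900 column still applies the 10% loss on top, so it is deliberately pessimistic.

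| Switchers | Switching reading | N = 1000 | N = 900 |
|---|---|---|---|
| Boosted from switch (5.4) | 15% in total | 99.1% / 98.8% | 98.4% / 97.7% |
| | median 4 months | 98.1% / 96.2% | 96.9% / 94.9% |
| | 15% per month | 98.2% / 96.6% | 97.1% / 95.4% |
| Kept in initial group | 15% in total | 98.2% / 98.2% | 97.1% / 96.1% |
| | median 4 months | 83.6% / 83.0% | 79.6% / 80.0% |
| | 15% per month | 85.2% / 84.6% | 81.3% / 81.0% |

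**Step 3: harsher readings.** Loss of 10% per month, N = 1000: 95–97% under section 5.4, and 77–79% with heavy switching kept in the initial group. The lowest value found under section 5.4 is 91.7% (N = 900, median 4 months, 10% loss per month, the enrolment month taken out of the 6 months).

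**Step 4: reproducing 80.0%.** Keep switchers in their initial group, let all controls switch at a median of 4 months, cut 1000 to 900 once for loss, and take the enrolment month out of the 6: 80.1%. No reading under section 5.4 comes near it.

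**Step 5: the effect that 80% power fits.** Under section 5.4 with N = 1000, the boosted rate is 1.44% per month (HR 0.574) if 15% switch in total, or 1.36% (HR 0.542) at a median of 4 months.

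**Step 6: 'evaluable'.** Enrolment stops at 1000, nobody is replaced, and participants whose enrolment serology shows past infection are discontinued. So 1000 can be evaluable only if no such participant is found. Those lost later are a separate matter: section 5.5.3 keeps them in the analysis, so they count until censored.

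**The case against.** The best defence is that 80.0% is a correct answer to another question. Section 6 names a plain log-rank test for the univariate analysis and reserves the time-dependent booster for the Cox model. The power statement mentions only the log-rank test and lists switching as an input. A log-rank by initial choice fits that wording and gives 80.1% in step 4. On this view there is no slip of arithmetic, only a mismatch between the power calculation and section 5.4. That is a fair account of how the figure may have arisen, but it does not rescue it. Section 5.4 is the only statement on how switchers are followed, and nothing in the protocol plans to keep them in their initial group. Step 4 also needs one particular reading of the switching line and 900 subjects, not the stated 1000.

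Three further points have some force. Combining N = 900 with a further 10% loss counts loss twice; the conclusion does not depend on that column. The 'evaluable' point is small, since known prior infection is already excluded and the documents give no number for the undetected remainder. Finally, all these figures are for an unadjusted test, and confounder adjustment in a self-selected cohort may cost precision, so a restated 98% must say so. The protocol does not, however, present 80.0% as an allowance for adjustment.

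The error is also on the safe side, which limits its consequence.

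**Conclusion.** The concern holds. Under the protocol's own rule for switchers, the listed inputs give about 96–99% power with 1000 subjects (about 95–98% with 900), against the stated 80.0%. About 80% requires heavy switching and analysis by initial group together; with only 15% switching in total, even that analysis gives about 98%. The switching line does not determine which reading is meant, and an evaluable 1000 does not fit enrolment of up to 1000.

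This rests on constant hazards, 10% loss over 6 months, switchers taking the boosted hazard at once, and the unadjusted log-rank test that the power statement names. The study is not underpowered on these inputs. What needs correcting is a relied-on figure, and possibly the comparison it was computed for.

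**What to change.** In sections 2 and 6:

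1. State whether 15% is the total or the monthly share of controls expected to switch, and what the 4-month median refers to.
2. Rerun power with switchers handled as in section 5.4 and restate it. For 1000 enrolled, 10% censored by 6 months and switchers counted as boosted from the booster date, the result for 2.5% against 1.0% per month is about 99% if 15% switch in total, or 96–98% if about half switch by 4 months. Give also the effect detectable with 80% power, about 1.4% against 2.5% per month (HR about 0.54–0.57). Say that these figures are for the unadjusted log-rank test.
3. If 80.0% came from analysis by initial group under heavy switching, say so and reconcile it with section 5.4 and the time-dependent model.
4. Replace 'evaluable' by 'enrolled', treat the 10% loss as censoring, and give the expected number discontinued for prior infection at enrolment, so that the power allows for them.

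The cost is one paragraph in two places and one rerun of the power calculation, with no change to enrolment or visits.

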## 7 Adverse Events

### 7.1 Adverse Event Definition

#### 7.1.1 Adverse Event

Any undesirable experience (sign, symptom, illness, abnormal laboratory value, or other medical event) occurring to a subject, that is considered related to the investigational treatment regimen prescribed as part of the clinical protocol, predefined in the clinical protocol and/or Instructions For Use, that is identified or worsens during a clinical study.

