## 2 Protocol Summary

OBJECTIVE	
Primary Objective  Examine the protection against any type of COVID-19 infection as confirmed by PCR testing or positive serology for N antigen during the follow up period.
 
Secondary Objectives  Evaluate the impact of a fourth dose on:
 
 
1. Symptomatic COVID 19 infection
 
2. COVID 19 infection requiring hospitalization
 
3. Antibody levels including IgG, IgA, IgM, binding and neutralizing activity and the avidity of the antibodies.
 

STUDY DESIGN	Prospective observational registry
OUTCOMES	
Primary Outcome  COVID-19 infection as confirmed by PCR testing or positive serology for N antigen during the follow up period. We hypothesize that booster of BNT162b2 vaccine in healthcare workers (HCW) will lower the rates of the COVID-19 infection as compared to HCW choosing not to receive the second booster.
 
Secondary Outcomes
 
 
1. Symptomatic COVID 19 infection
 
2. COVID 19 infection requiring hospitalization
 
3. Levels of binding and neutralizing activity and avidity of the antibodies
 
4. Composite endpoint of serious adverse events during 14 days following the booster vaccination
 

SAMPLE SIZE CONSIDERATIONS	
We aim to enroll up to 1000 subjects. The following assumptions were used to estimate the power of the analysis.
 
 
• The proportion of the HCW choosing to receive the second booster is 60%
 
• The expected monthly infection rate of 2.5% in the non-vaccinated group
 
• Expected monthly infection rate of 1.0% in the treatment group
 
• Median follow-up until switching to the booster administration in the non-vaccinated group (15%) of 4 months
 
• Type I error (<math>\alpha</math>) = 0.025 (one-sided)
 
• Log-rank test
 
• Enrollment period of 1 month
 
• Lost to follow-up of 10%
 
 
An evaluable sample size of 1000 subjects provides 80.0% power to reject the null hypothesis, signifying the booster strategy is superior to the comparison group at 6 months post-vaccination.

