STUDY PROCEDURES	
Screening and Enrollment
 
The following will take place at this visit:
 
 
• Confirmation of eligibility and informed consent will be signed.
 
• Demographics and medical history will be recorded.
 
• COVID-19 questionnaire regarding exposure and symptoms.
 
• Blood draw of three 5 ml vials, for antibody testing.
 
• Blood drawn for PBMC and antibody testing: 
 
◦ Will be ONLY at Soroka Medical Center.
 
◦ 150 subjects will be selected randomly. Subjects participating in this part will have 30 ml (3 vials of 9 ml and 1 vial of 3 ml) of blood drawn for PBMC and antibody testing. Others will have blood draw of three 5 ml vials, for antibody testing.
 
 
 
• A nasal and mouth swab will be performed for IgA, IgG and IgM levels testing
 
 
Visit 2 –6
 
 
• COVID-19 questionnaire regarding exposure and symptoms. Blood draw of 3 vials of 5 ml for antibody testing,
 
• Blood drawn for PBMC and antibody testing: 
 
◦ Will be ONLY at Soroka Medical Center. Subjects who were not part of the PBMC group and are willing to participate, will be asked again to sign informed consent.
 
◦ Subjects participating in this part will have 30 ml (3 vials of 9 ml and 1 vial of 3 ml) of blood drawn for PBMC and antibody testing. Others will have blood draw of three 5 ml vials, for antibody testing.
 
 
 
• A nasal and mouth swab will be performed for IgA, IgG and IgM levels testing
 
• Adverse events following vaccination and changes in medications (chronic and/or Immune suppression medication) will be collected
 

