LABORATORY TESTING	
 
From each HCW at each visit the following tests will be performed:
 
The Platelia SARS-CoV-2 Total Ab assay by Bio rad, is a semi-quantitative in vitro diagnostic test, in a one-step antigen capture format, for the detection of IgM/IgA/IgG antibodies to the SARS-CoV-2 in human serum and plasma (EDTA, heparin, ACD or citrate) specimens. This assay will be performed at SMC virology laboratory (head-[name]).
 
Antibody profiling of blood and nasal samples will be tested using antigen microarrays, this will be performed by using chip antigen microarrays spotted with various coronavirus antigens, as well as antigens of other common respiratory pathogens. This assay will be performed at [name] laboratory at Ben-Gurion University of the Negev.
 
On select samples from each visit neutralization assays for SARS-CoV-2 virus variants will be performed. Each sample selected will be tested for its ability to inhibit infection of target ACE2-expressing cells by reporter pseudoviruses that express the spike protein of either Delta or Omicron Variant of Concern. This assay will be performed at [name] laboratory at Ben-Gurion University of the Negev.
 
Blood samples for PBMC'S will be stored at [name] laboratory at Ben-Gurion University of the Negev for future research.
 

DATA TO CAPTURE	
The following data will be collected:
 
 
Demographic data: age, sex, country of birth, healthcare profession, direct contact with covid subjects in working capacity.
 
Detailed medical history, including but not limited to past illness with COVID, malignancy, diabetes, renal failure, heart disease, hypertension, history of stroke, rheumatological illness.
 
Current medications used and medications used for more than one week in the past three months.
 
Any adverse event during the study as a result of vaccination.
 

DATA MANAGEMENT AND ANALYSIS	
The study will be overseen and managed by the Soroka Clinical Research Center.

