### **5.8.2 Visit 2 –6**

- COVID-19 questionnaire regarding exposure and symptoms. Blood draw of three vials of 5 ml for antibody testing,
- Blood drawn for PBMC and antibody testing:
  - Will be at ONLY at Soroka Medical Center. Subjects who were not part of the PBMC group and are willing to participate, will be asked again to sign informed consent.
  - Subjects participating in this part will have 30 ml (3 vials of 9 ml and 1 vial of 3 ml) of blood drawn for PBMC and antibody testing. Others will have blood draw of three 5 ml vials, for antibody testing.
- A nasal and mouth swab will be performed.
- Adverse events following vaccination and changes in medications (chronic and/or Immune suppression medication) will be collected

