#### 7.1.2 Treatment Related Adverse Event

A treatment related adverse event is defined as any adverse event, for which a causal relationship between the treatment and the event is at least a reasonable possibility, i.e., the relationship cannot be excluded.

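### The adverse event definition and the data-capture lists depend on attribution to treatment, but the 14-day serious adverse event outcome does not, so unrelated serious events could go unrecorded

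*Protocol*

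**What the plan says.** Five parts of the protocol bear on which adverse events are recorded and counted.

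- **Definition.** Section 7.1.1 makes relatedness part of what an adverse event is: the event must be one "that is considered related to the investigational treatment regimen prescribed as part of the clinical protocol". The same sentence adds that it be predefined in the protocol or in instructions for use.
- **Related events.** Section 7.1.2 defines a treatment-related event as "any adverse event, for which a causal relationship between the treatment and the event is at least a reasonable possibility".
- **Serious events.** Section 7.1.3 defines a serious adverse event by subject outcome (death, hospitalization and so on) and says such events enter the analysis. It deals separately with side effects caused by vaccination, which go to the Ministry of Health. Secondary outcome 4 in the Protocol Summary is "Composite endpoint of serious adverse events during 14 days following the booster vaccination". Neither carries a condition on cause.
- **Collection.** Data to Capture in the Protocol Summary and section 5.11.2 both list "Any adverse event during the study as a result of vaccination". Section 5.8.2 and its summary copy say "Adverse events following vaccination and changes in medications (chronic and/or Immune suppression medication) will be collected". The schedule in section 5.3 has an adverse events row with no qualifier, marked at enrollment and at every visit. Section 7.2 treats pain or hematoma from blood draws and swabs as adverse events.
- **Reporting.** Section 6 plans no test for outcome 4. Its general rule is "Categorical variables will be presented using frequency distributions and cross tabulations with numbers and percent per group".

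**The concern.** Outcome 4 is the protocol's only safety outcome. As worded, it counts every serious event in the 14 days after the booster. The text that tells sites what an adverse event is, and what to put on the case report form, adds a causal filter that the outcome does not have.

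A serious event on day 10 that the investigator judges unrelated therefore qualifies under 7.1.3 and outcome 4, fails 7.1.1, and appears on neither capture list. A site could omit it while following the written capture rule. If that happened, outcome 4 would become partly a related-only count, resting on judgments by staff who know who was boosted. An analysis plan could not repair this later, because it cannot bring back events that were never collected.

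**Working it through.** **Step 1: compare the wording.** Take a serious event within 14 days of the booster, judged unrelated to it.

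| Place | Test applied | Event included? |
|---|---|---|
| Secondary outcome 4 | time window | yes |
| 7.1.3 | subject outcome | yes |
| 5.3 schedule row | none stated | yes, unless 7.1.1 governs the term |
| 5.8.2 and summary copy | after vaccination | yes, unless 7.1.1 governs the term |
| 7.1.1 | related to a prescribed regimen | no |
| 5.11.2 and summary copy | caused by vaccination | no |

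The collection wording is thus causal in one pair of places, temporal in another pair and unqualified in a fifth. Section 7.2 adds procedure effects, which the causal wording also leaves out.

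**Step 2: two readings of 7.1.1.** Section 6 describes an observational registry in which workers choose the booster, so the protocol prescribes no regimen. Strictly read, no event after the booster qualifies. Read with the booster as the regimen, only related events qualify. The figures below use this second, milder reading.

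**Step 3: the denominator (section 6).**
- Boosted at entry: 60% of 1000 = 600, which leaves 400 controls.
- If the 15% in the assumption about switching is the share of controls who switch: 600 + 0.15 × 400 = 660.

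**Step 4: weight of one missed event.** 1/660 = 0.15% and 1/600 = 0.17%. This step needs no outside rate.

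**Step 5: how many events might be at stake (illustration).** The protocol gives no background rate. Assume an all-cause serious event rate of 3% to 8% per year and Poisson counts with mean m.
- Expected events in 14 days: 600 × 0.03 × 14/365 = 0.69, up to 660 × 0.08 × 14/365 = 2.03.
- As a percentage of boosted subjects: 3% × 14/365 = 0.12%, up to 8% × 14/365 = 0.31%.
- Chance of at least one, 1 − exp(−m): 0.50 to 0.87.

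Section 7.1.2 treats an event as related unless a link can be excluded, so perhaps only part would be judged unrelated. Assume 25% to 100%.
- Events that could go unrecorded: 0.25 × 0.69 = 0.17, up to 1.00 × 2.03 = 2.03.
- Chance of at least one: 1 − exp(−0.17) = 0.16, up to 0.87, before any recovery from records.

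The upper end combines the largest denominator, the highest rate and every event judged unrelated. It is a bound under these assumptions, not a forecast.

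**The case against.** The strongest reply is that the provisions specific to serious events are already sound. Outcome 4 and 7.1.3 carry no causal condition, the schedule row is unqualified, and visits 2 to 6 collect by time. On this view 7.1.1 is template wording and the capture list a loose summary line. This stands in part: it shows that the intent was probably to collect by time, and it is why a reader should not infer that outcome 4 will certainly be under-counted. It does not remove the conflict, because nothing says which wording governs, and the restrictive wording sits in the formal definition and in the list of data to collect.

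Four further points have weight.

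- **Other capture routes.** COVID-19 hospitalizations are recorded without attribution as secondary outcome 2, so they should not be lost this way. Section 5.11.2 allows that data "will be collected through the computer services database", and section 8.2 mentions medical records, so other events may be recoverable. Neither section provides for an all-cause extraction.
- **Assumed rates.** The rates in step 5 are not from the protocol. The subjects are employed healthcare workers, with malignancy and recent immunosuppression among the exclusions, so the upper rate is doubtful.
- **Section 7.1.2.** A reader might infer that it contradicts 7.1.1. It does not: if every adverse event is already related, 7.1.2 is merely redundant.
- **Inherited relatedness.** A reader might also infer that a serious adverse event, as a kind of adverse event, carries the condition in 7.1.1, so that outcome 4 is meant as a related-only count. Section 7.1.3 does not say so. It confines attribution wording to the Ministry of Health report.

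**Conclusion.** The point holds as an internal inconsistency with a small possible effect. The definition in 7.1.1 and both capture lists depend on attribution, outcome 4 and 7.1.3 do not, and the other collection passages follow neither pattern consistently. The text permits under-counting of outcome 4 but does not make it inevitable.

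The one figure that rests on the protocol's own numbers is 0.15 to 0.17 percentage points per missed event, given 600 to 660 boosted subjects; the 660 depends on how the 15% is read. The range of 0.17 to 2.03 unrecorded events rests wholly on an assumed yearly rate and an assumed share judged unrelated. The inconsistency itself needs neither assumption. Outcome 4 is a descriptive secondary outcome, and nothing here touches the primary outcome or the power. It is worth correcting because the outcome is the only safety measure and the correction is nearly free.

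**What to change.** - **7.1.1:** delete the relatedness condition and also the phrase requiring the event to be predefined in the protocol or instructions for use, which would otherwise remain as a second restriction. Keep relatedness as a recorded attribute under 7.1.2.
- **5.11.2 and Data to Capture in the summary:** replace "Any adverse event during the study as a result of vaccination" with wording that covers every adverse event in the study, including all serious ones with onset dates, whatever the attribution, with relatedness to vaccination or to study procedures recorded separately.
- **5.8.2 and its summary copy:** bring the wording into line with the unqualified row in 5.3, so that procedure effects in unboosted subjects (7.2) are covered too.
- **Outcome 4:** state that it is reported as all-cause serious adverse events within 14 days of the booster, as number and percent, with the related-only count as supportive.

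The cost is wording in five places plus one sentence for outcome 4, and a few more events to record at visits already scheduled. The change does not give the registry power to detect a rise in serious events.
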